13. DIRECT ACCESS TO SOURCE DATA/DOCUMENTS

13.1. Study Monitoring

The conduct of the study will be closely monitored by the Aclaris Therapeutics, Inc. study monitor /CRO to verify adherence to ICH Good Clinical Practice (GCP) guidelines, applicable SOPs, the protocol, other written instructions and regulatory guidelines.

The investigator will allow the Aclaris Therapeutics, Inc. representative, designee and/or any regulatory agency to have direct access to all study records, CRFs, corresponding subject medical records, study medication dispensing records and study medication storage area, and any other documents considered source documentation. The investigator also agrees to assist the representative, if required.

13.2. Audits and Inspections

The study is conducted under the sponsorship of Aclaris Therapeutics, Inc. in compliance with the applicable regulatory requirements as well as applicable ICH guidelines, Helsinki Declaration, and in respect of the Aclaris Therapeutics, Inc. and/or sub-contractor SOPs for study conduct and monitoring.

Audits may be carried out by Aclaris Therapeutics, Inc. or its representatives and inspections may be performed by regulatory authorities or IRB/ECs before, during or after the study. The investigator will provide the auditing/inspecting group direct access to all study records (*e.g.*, CRFs, subject medical records, study medication dispensing records) and the investigational center study facilities. The investigator and study staff will be available and will assist the auditing/inspecting groups as appropriate.

The investigator should contact Aclaris Therapeutics, Inc. immediately if contacted by a regulatory agency about an inspection.

13.3. Institutional Review Board (IRB)

This protocol and any accompanying material, including information that will be provided to prospective subjects (such as advertisements, subject information sheets, or study descriptions used to induce study participation or obtain informed consent) must be submitted to the IRB for approval. Approval of each such submission must be obtained from the committee before it may be used in the study and must be documented in a written notification to the Investigator specifying the protocol number, protocol version, documents reviewed, and date on which the committee met and granted the approval. In particular, each informed consent document must bear clear evidence (written, stamp, date of approval, etc.) of IRB approval before it may be presented to prospective (or ongoing, as appropriate) study subjects for signature.

Written evidence of the approval must be made available to the Sponsor. Any modifications made to the protocol and of correspondingly modified informed consent documents made after receipt of IRB approval must also be submitted to the committee for approval before implementation unless the modification is made on an emergency basis to protect the welfare of study subjects. In the latter case, the IRB must be notified promptly, and their written approval must be obtained as soon after the fact as possible.

Appropriate reports on the progress of the study will be made to the IRB and the Sponsor by the Investigator in accordance with applicable regulatory regulations and in conformity with policies established by both the IRB and the Sponsor. The shortest time interval between required reports required by either party or by regulations will prevail.

The Investigator at each investigative site, or his/her nominee, will be responsible for reporting any SAEs to the IRB as soon as possible, and in accordance with the guidelines of the IRB.

The Sponsor will be responsible for reporting all serious, life threatening or fatal adverse study drug events with a causal relationship to the study drug to appropriate regulatory agencies within their required timelines.

The Investigator is responsible for obtaining written, informed consent(s) from each prospective subject interested in participating in this study before performing any study-related procedures. Written informed consent must be obtained after adequate, thorough, and clear explanation of the aims, methods, objectives, and potential hazards of the study, as well as any use of the subject's genetic information from the study. The Investigator must use the most current Central IRB-approved consent form for documenting written informed consent. Each informed consent will be appropriately signed and dated by the subject. The investigational site must retain the original signed consent and provide a copy to the subject.

14. QUALITY CONTROL AND QUALITY ASSURANCE

14.1. Protocol Amendments

No changes from the final approved (signed) protocol will be initiated without the prior written approval or favorable opinion of a written amendment by the IEC/IRB, except when necessary to eliminate immediate safety concerns to the subjects or when the change involves only logistics or administration. The principal investigator and the sponsor will sign the protocol amendment.

14.2. Protocol Deviations, Violations, and Exceptions

A protocol **deviation** is non-adherence to protocol-specific study procedures or schedules that does not involve inclusion/exclusion criteria, primary objective variable criteria, and/or GCP guidelines. Deviations are considered minor and do not impact the study.

A protocol **violation** is defined as any divergence from the protocol-specific inclusion/exclusion criteria, subject is administered a prohibited medication during the active protocol treatment period, primary objective variable criteria, and/or GCP guidelines. Protocol violations will be identified and recorded, by study center personnel, on the CRF.

As a matter of policy, sponsor/CRO will not grant **exceptions** to protocol-specific entry criteria to allow subjects to enter a study. If under extraordinary circumstances such action is considered ethically, medically, and scientifically justified for a particular subject, prior approval from sponsor/CRO and the responsible IRB/IEC, in accordance with the Sponsor/CROs Standard Operating Procedure (SOP), is required before the subject will be allowed to enter the study. If investigative center personnel learn that a subject who did not meet protocol eligibility criteria was entered in a study (a protocol violation), they must immediately inform sponsor/CRO. Such subjects will be discontinued from the study, except in a rare instance following review and written approval by sponsor/CRO and the responsible IRB/IEC, according to the applicable SOP

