6.4. Dose Adjustment Criteria

If a subject refuses the initial treatment or retreatment, the investigator must report the visit number, visit date, target SK number(s) that the subject refused to allow treatment for and the reason for the refusal in the subject's CRF.

If the subject's refusal is associated with an AE, the investigator must also report the event on the appropriate CRF.

The subject must have the Visit 2 initial study medication treatment to all target SKs to remain in the study.

The subject does not need to be removed from the study based solely on her/his refusal to have a study medication retreatment at Visit 5 or Visit 7.

Table 3: Study Design and Schedule of Assessments

Visit	Visit 1	Visit 2	Visit 3	Visit 4	Visit 5	Visit 6	Visit 7	Visit 8	Visit 9	Visit 10	Visit 11
Treatment Day	Day -13 - 0	Day 1	Day 2	Day 8	Day 15	Day 22	Day 29	Day 36	Day 57	Day 85	Day 113
Visit Window	N/A	N/A	N/A	± 1 day	± 1 day	± 1 day	± 1 day	± 1 day	± 7 days	± 7 days	± 7 days
Informed Consent	X										
Inclusion/ Exclusion ¹	X	X									
Subject Identifier ²	X										
Dermatological Medical History	X										
Demographics	X										
Fitzpatrick Skin Type Assessment ³	X										
Vital Signs ⁴	X	X			X		X			X	X
Prior Medications/Therapies ⁵	X										
Target and Non-Target SK Identification ⁶	X										
Physician’s Lesion Assessment ⁷	X	X	X	X	X		X			X	X
SK Dimensions ⁸	X	X	X	X	X		X			X	X
SK Photography ⁹	X	X ¹⁰	X ¹¹	X	X ¹⁰	X	X ¹⁰	X	X	X	X
Study Medication Application ¹²		X			X		X				
Subject Satisfaction Assessment ¹³		X	X			X		X		X	X
Concomitant Therapies ¹⁴	X	X	X	X	X	X	X	X	X	X	X
Adverse Events ¹⁵		X	X	X	X	X	X	X	X	X	X

¹Subject inclusion/exclusion criteria will be reassessed prior to enrollment during Visit 2.

Protocol A-101-SEBK-402

²Investigational sites will assign a unique five-digit subject identifier to each subject at Visit 1, formatted as NN-NNN where the first 2 digits are the site number, and the final 3 digits are the subject number that must be assigned in ascending numerical order (using leading zeroes, as appropriate). This subject identifier will be used in all study documentation for the duration of the study.

³Each subject's skin must be assessed during Visit 1 using the Fitzpatrick Skin Type Assessment. Refer to Table 6 for the scale.

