¹²A-101 40% will be applied to each target and non-target SK by a study trained healthcare provider at the site. Each target and non-target SK will be treated with A-101 40% following confirmation of subject eligibility and study enrollment at Visit 2. If a target or non-target SK meets the criteria for retreatment as defined in Section 9.5, the SK will be retreated at Visit 5 and Visit 7. Following application of A-101 40%, subjects must NOT wash/submerge a target and non-target SK for at least 6 hours and they must NOT apply any topical products to any target or non-target SK for at least 6 hours.

¹³Subjects will be asked to assess how satisfied they are with the treatment experience they received for the target and non-target SKs at the specified visits. On Visit 2 the subject will complete the assessment prior to application of A-101 40%. On Visit 3 the subjects will complete the assessment approximately 24 hours after the treatment. On Visit 6 and Visit 8 the subjects will complete the assessment approximately 1 week after the treatment, only if the subject received treatment on Visit 5 or Visit 7. The subject will complete the assessment during the Visit 10 and Visit 11.

¹⁴All concomitant therapies including (topical and oral) prescription medications, over the counter medications, natural supplements and non-drug therapies including chiropractic, physical therapy, and energy-based therapy must be documented in the subject CRF. Subjects must not apply any topical products (*e.g.*, moisturizers, sunscreen, etc.) to their target and non-target SKs within 12 hours prior to any study visit.

¹⁵The reporting period for SAEs begins when the subject signs the informed consent form. Refer to Section 11.6 for instructions on the reporting of SAEs. Non-serious clinical adverse events will be collected following the application of the study medication at Visit 2 and continue through Visit 11. All safety reporting (AEs and SAEs) will conclude at Visit 11.

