7.4. Withdrawal Procedures

If a subject withdraws from the study prior to Visit 11, the reason for and the date of withdrawal from the study must be recorded on the eCRF. If the reason for withdrawal is an adverse event, monitoring of the subject will continue until the event has resolved or stabilized, until the subject is referred to the care of a local health care professional, or until a determination of a cause unrelated to the study drug or study procedure is made.

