7.5. Subject Replacement

If a subject is enrolled to the study but does not receive a dose of study drug, then the subject may be replaced.

Subjects that are determined to be screen failures may be rescreened for the study and if determined to be eligible for the study they may be enrolled using the same subject identifier and must sign a new informed consent form.

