11.6. Reporting Adverse Events

At each post enrollment visit, the investigator or designee will question the subject to elicit AEs using a non-directive question such as “Has there been any change in your health since the previous study visit?”

The investigator or designee will monitor the subject for at least 20 minutes after the Treatment Completion Time at Visit 2, and if applicable at Visit 5 and Visit 7 to elicit AEs in a similar manner.

If appropriate, based on the subject’s response to non-directed questioning regarding AEs, the investigator or designee will follow-up with directed questions and appropriate evaluations.

Non-serious AEs should be recorded starting with the subject’s first study medication treatment at Visit 2 and continuing through Visit 11.

All SAEs regardless of relationship to study medication must be collected and reported to Aclaris Therapeutics, Inc. from the time the Informed Consent is signed through Visit 11.

Upon becoming aware of a SAE the investigator must:

1. Take the appropriate medical action to ensure the subject’s safety
2. Immediately inform the Safety Monitor of the SAE:

[name]
Aclaris Therapeutics, Inc.
[name]
[name]
[contact]
Serious Adverse Event [contact]
Email: [contact]

3. Within 24-hours of becoming aware of the event, a SAE report form, an AE CRF and any other relevant information (*e.g.*, concomitant medication CRF, medical history CRF, laboratory test results) must be faxed to the SAE Fax line listed above.
4. Monitor and document the progress of the SAE until it resolves or, if not resolved after the subject’s last study visit, until in the opinion of the investigator the SAE reaches a clinically stable outcome with or without sequelae AND the investigator and Safety Monitor agree that the SAE is satisfactorily resolved.
5. Inform the Safety Monitor of SAE updates by telephone followed by an SAE form update sent by fax or by e mail.

6. Comply with the appropriate regulatory requirements and Aclaris Therapeutics, Inc. instructions regarding reporting of the SAE to the responsible Institutional Review Board (IRB) or Ethics Committee (EC).

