11.7. Withdrawal Due to an Adverse Event

Any subject who experiences an adverse event may be withdrawn from study drug at any time at the discretion of the investigator. If a subject is withdrawn wholly or in part because of an adverse event, both the adverse events page and termination page of the CRF will be completed at that time. The subject will be monitored until the event has resolved or stabilized, until a determination of a cause unrelated to the study drug or study procedure is made, or until the subject is referred to the care of a local health care professional. The investigator must inform the medical monitor as soon as possible of all subjects who are being considered for withdrawal due to adverse events. Additional reports must be provided when requested.

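### Section 14.2 by default takes a treated subject found ineligible out of the study, not only off dosing, so no scheduled visit remains to collect Day 85 and Day 113 data or new adverse events.

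*Protocol*

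**What the plan says.** Protocol 14.2 requires a site that discovers an ineligible subject was entered to tell the sponsor/CRO at once. It then sets the default: "Such subjects will be discontinued from the study, except in a rare instance following review and written approval". The approval must come from sponsor/CRO and the responsible IRB/IEC, under an SOP that is not in the documents.

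The follow-up provisions around that rule are these:

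- Protocol 7.4 asks for the reason and date of any withdrawal before Visit 11. Continued observation is tied to one reason: "If the reason for withdrawal is an adverse event, monitoring of the subject will continue until the event has resolved or stabilized".
- Protocol 11.7 has a similar trigger: "If a subject is withdrawn wholly or in part because of an adverse event".
- Protocol 11.6, step 4, covers a serious event already known: "Monitor and document the progress of the SAE until it resolves". Section 11.6 also requires every SAE to be collected through Visit 11.
- Table 3, footnote 15: "Non-serious clinical adverse events will be collected following the application of the study medication at Visit 2 and continue through Visit 11". Table 3 has no early-termination visit.
- SAP 3.8.1 has all subjects assessed for AEs until 30 days after the last treatment.

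On who counts, SAP 3.2.1 defines enrolment as having at least one treatment applied and uses all enrolled subjects for every analysis. Replacement is narrower (Protocol 7.5): "If a subject is enrolled to the study but does not receive a dose of study drug, then the subject may be replaced".

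Elsewhere the protocol separates dosing from participation. Section 6.4 says of Visits 5 and 7: "The subject does not need to be removed from the study based solely on her/his refusal to have a study medication retreatment".

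**The concern.** An eligibility error found after Visit 2 does not undo the exposure. Under 6.4 a subject must have had all target lesions treated at Visit 2 to stay in, so an affected subject has at least 3 lesions exposed to 40% hydrogen peroxide, two of them on the face. There may be good reason to stop further applications. There is less reason to stop looking at the subject.

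The default in 14.2 does both. If it is followed as written, a willing subject is lost to the two time points named for the primary evaluation, Day 85 and Day 113. The subject remains in the ITT set without those values, and 7.5 provides no replacement for a subject who has been dosed. The SAP states no method for missing values. What is at stake is completeness and safety observation in a study of 30.

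**Working it through.** The plan gives no figure on this point to reproduce: 30 subjects are stated without power, effect size or an allowance for loss. The check has three parts.

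**1. Does any provision restore visits after removal solely for ineligibility?**

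- 7.4 and 11.7 apply only when an AE is, wholly or partly, the reason for withdrawal.
- 11.6 step 4 follows an SAE already known. The general duty in 11.6 to collect all SAEs through Visit 11, and the 30-day AE window in SAP 3.8.1, have no stated exception for removed subjects. Neither comes with a visit or contact after removal.
- Table 3 schedules nothing for a subject who has left.
- 7.3 is softer: it is permissive and speaks of removal from study therapy. It lists a *change* in compliance with a criterion, which differs from never having met it. It does not override the mandatory wording of 14.2.

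So no scheduled visit remains.

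**2. What is lost per affected subject?** Inputs are the nominal days and visits in Table 3. The comparison is with follow-up that continues without further dosing.

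| Found just after | Days lost | Visits lost | PLA visits lost | Satisfaction assessments lost (up to) |
|---|---|---|---|---|
| Visit 2 (Day 1) | 113 − 1 = 112 | V3–V11 = 9 | V3, 4, 5, 7, 10, 11 = 6 | V3, 10, 11 = 3 |
| Visit 5 (Day 15) | 113 − 15 = 98 | V6–V11 = 6 | V7, 10, 11 = 3 | V6, 10, 11 = 3 |
| Visit 7 (Day 29) | 113 − 29 = 84 | V8–V11 = 4 | V10, 11 = 2 | V8, 10, 11 = 3 |

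The Visit 6 and Visit 8 surveys are completed only if the subject was treated at Visit 5 and Visit 7 respectively. Any removal before Day 85 loses both Day 85 and Day 113. Under the SAP 3.8.1 window, up to 30 days of AE collection are left without a visit, instead of 84 to 112.

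**3. What does that do at study level?** The documents give no rate for ineligibility found after dosing. Assume k = 0, 1, 2 or 3 of 30, each lost early.

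- Upper bound for an AE with zero events (one-sided 95%): 1 − 0.05^(1/n), with n = 30 − k. This gives 9.5%, 9.8%, 10.1% and 10.5% for n = 30, 29, 28 and 27. It treats a removed subject as wholly unobserved, which is pessimistic.
- Mean per-subject percent of lesions clear, range 0 to 100: the undetermined part is at most 100k/30 = 0, 3.3, 6.7 or 10.0 percentage points.
- Target lesions without a Day 113 PLA: 3k of 3 × 30 = 90, that is 0, 3, 6 or 9.

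For scale only: the introduction reports discontinuation for protocol violation in 2.2% (study 301) and 4.5% (study 302) of A-101 subjects. These rates are not limited to eligibility. If they applied here, the expected number would be 30 × 0.022 = 0.66 to 30 × 0.045 = 1.35. The chance of at least one, 1 − (1 − p)^30, would be 49% to 75%, and of at least two 14% to 39%.

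**The case against.** The strongest reply is that the loss is inferred from silence. Section 14.2 does not say that follow-up ends, and the protocol uses its terms loosely: 7.3 moves between study therapy and study, and 11.7 speaks of withdrawal from study drug. Section 11.6 and SAP 3.8.1 state collection duties with no exception for removed subjects. The cited SOP may add protection, and 14.2 allows an individual exception.

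Part of this stands. A reader might infer that 14.2 cancels all safety collection for a removed subject. The documents do not support that: the SAE duty through Visit 11 and the 30-day AE window remain on paper. What is missing is any visit at which to carry them out. The loose terms do not rescue 14.2, whose own wording is study-level and mandatory. The SOP cannot be judged, but 14.2 cites it for the rare exception and makes removal the default.

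A second objection also stands: keeping every treated subject without conditions would be unsafe. Someone who failed inclusion criterion 1 may not have given valid consent. Someone whose lesion proves atypical or not an SK would remain under the Section 8.4 bans on other treatments for it, and the PLA would have doubtful meaning there. The comparison with 6.4 is imperfect too, since a subject who refuses retreatment is eligible and validly consented. It shows only that follow-up without dosing is workable.

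Finally, the event should be uncommon. Table 3, footnote 1, says "inclusion/exclusion criteria will be reassessed prior to enrollment during Visit 2", and PLA and diameter are reassessed before dosing. Late discovery remains possible because several criteria rest on history, such as cryosurgery timing and recent trial participation.

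**Conclusion.** The point holds and is minor. Following 14.2 as written ends scheduled observation of a treated subject for an entry error, while the SAP keeps that subject in the analysis set. For each affected subject the loss is substantial: 84 to 112 days and both primary time points, if found just after a treatment visit. For the study it is small: the study is descriptive and open-label, without inferential safety testing, and the figures above barely move.

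This rests on three assumptions: that 14.2 is applied as worded, that the unseen SOP adds no follow-up, and that the number affected is about 0 to 3 of 30, which the documents neither give nor exclude.

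A reader might go further and infer that the rule biases the satisfaction or clearance results. Nothing in the documents links ineligibility to outcome, so no direction can be stated. The satisfaction analysis belongs to a separate plan that is not available (SAP 3), and that plan may deal with missing subjects. Nor should the protocol-violation rates of the earlier studies be read as the expected rate here.

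**What to change.** Replace the last sentence of Protocol 14.2 with:

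> A subject found ineligible before receiving study medication is discontinued from the study. A subject found ineligible after receiving study medication receives no further applications, unless sponsor/CRO and the responsible IRB/IEC approve in writing, but remains in scheduled follow-up through Visit 11 (AEs, PLA where the lesion is an SK, satisfaction), provided the subject has valid consent and does not withdraw it, and unless the investigator or medical monitor judges that continued participation is not in the subject's interest. The Section 8.4 restrictions do not prevent medically needed care of a lesion found atypical or not an SK.

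The duty to inform sponsor/CRO immediately stays as it is.

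The cost is one amendment under 14.1, with IRB approval and signatures by the principal investigator and sponsor. It needs no new visits, staff, subjects or assessments. The downside is that a few ineligible subjects, some with a shortened regimen, contribute Day 85 and Day 113 data to the ITT summaries. They already belong to that set under SAP 3.2.1, can be identified from the violations recorded on the CRF, and can be flagged in the tables.
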